7.6 MENSTRUAL BLEEDING CALENDAR

Subject Number: _____

Date Calendar Given to Subject/Parent or Legal Guardian: _____

Instructions:

- Circle the dates when vaginal bleeding requires protection GREATER than a panty shield.
- Mark "S" on the dates when spotting occurs that DOES NOT require protection greater than a panty shield.
- Place no marks on the calendar on the dates when there's no bleeding or spotting.
- Initial this page (person who completes the calendar).

See Example Calendar Below:

November 2017						
S	M	T	W	T	F	S
			1	2	3	4
5	6	7	8 S	9 S	(10)	(11)
12 S	13	14	15	16	17	18
19	20	21	22	23	24	25
26	27	28	29	30		

Initials and date: _____

## **3.0                   Introduction**

This statistical analysis plan (SAP) describes the statistical analysis to be completed by AbbVie Clinical Statistics Department for leuprolide acetate Study M16-904.

The SAP will provide details to further elaborate statistical methods as outlined in the protocol and will describe analysis conventions to guide the statistical programming work. Unless noted otherwise, all analyses will be performed using SAS version 9.4 or later (SAS Institute Inc., Cary, NC 27513) under the UNIX operating system.

## **4.0                   Study Background**

### **4.1                   Objective**

#### **Primary objective:**

- To assess the safety and efficacy of LA 45 mg 6-month depot formulation for the treatment of CPP in children who are either naïve to treatment with a GnRHa or who have been previously treated with a GnRHa.

#### **Secondary objective:**

- To evaluate the pharmacokinetic profile and pharmacodynamics of leuprolide following intramuscular administration of the LA 45 mg 6-month depot formulation in subjects with CPP.

## **4.2                   Study Design**

This is a Phase 3, open-label, 2-part study in which the safety, efficacy, and pharmacokinetics/pharmacodynamics of a leuprolide acetate 45 mg 6-month (LA 45 mg 6-month) formulation will be evaluated in children with CPP. Part 1 (initial treatment) will be 52 weeks in duration, including a 4-week Screening Period and 48-week treatment period. Part 2 (a long-term extension of Part 1) will be 108 weeks in duration, including a 96-week treatment period and a 12-week follow-up period.

#### **4.2.1 Study Design and Design Diagram**

The total duration of the study (Parts 1 and 2) will be 160 weeks as follows:

- Part 1: 52 weeks (4-week screening period + 48-week treatment period)
- Part 2: 108 weeks (additional 96-week treatment period + 12-week follow-up period)

**Part 1:** The safety, efficacy, pharmacokinetics, and pharmacodynamics of the LA 45 mg 6-month dose will be evaluated in subjects with CPP from Baseline to Week 48. In all subjects, blood samples for efficacy assessments (analysis of LH, testosterone concentrations [males], and estradiol concentrations [females]) will be collected at Baseline and at Weeks 1, 4, 12, 20, 24, 44, and 48 after dosing. In the first subjects who are enrolled (20 subjects total, with at least 8 naïve and 8 previously treated), concentrations of leuprolide will be measured at each study visit following administration of LA 45 mg 6-month to characterize the leuprolide concentration-time profile, rate of absorption, and pharmacokinetic/pharmacodynamic relationship of leuprolide and LH. Investigative sites will be notified when the pharmacokinetic subset has been fulfilled.

[figure not shown]
Leuprolide and appropriate measures of efficacy (LH, estradiol in females, testosterone in males) will be monitored upon data availability to evaluate the appropriateness of the 24-week dosing interval for the 6-month formulation for CPP.

**Part 2:** Following completion of Part 1 (the initial 48-week treatment period) assessments, subjects will continue to Part 2 of the study (extension period) to evaluate long-term administration of LA 45 mg 6-month (up to 24 months). Study visits during the extension period will start at Week 48 and continue once every 24 weeks for 96 weeks (24 months) until the subject discontinues treatment of LA 45 mg 6-month or withdraws from the study. Subjects will be assessed for continued maintenance of LH suppression and safety throughout this extension period.

A schematic of the study is shown in [Figure 1](#).

**Figure 1. Study Schematic**

Children with CPP (N = ~40)

AOC = acute-on-chronic; E2 = estradiol; T = testosterone

a. At the beginning of Part 2, subjects will be randomly selected for AOC biochemical assessments 48 hours following the injection at Weeks 48, 72, 96, and 120.

Note: Week 0 = Day 1 (Baseline).

Note: See Operations Manual for details.

#### 4.2.2 Variables Used for Stratification at Enrollment

All subjects in this study will receive the same treatment; therefore, no treatment randomization will be performed. A minimum of 15 of whom must be naïve to treatment with a GnRHa, and a minimum of 15 of whom must have been previously treated with a GnRHa.

At the beginning of Part 2, using the IRT system, half of the subjects will be randomly selected to have AOC biochemical assessment 48 hours after the injection at Weeks 48, 72, 96, and 120. Randomization will be stratified based on previous GnRHa treatment status (treatment-naïve or previous treated with a GnRHa). The randomization schedule will be generated and kept by the statistics department at AbbVie and a copy will be forwarded to the IRT provider.

## **4.3 Endpoint**

Efficacy endpoints will be based on hormonal suppression. Stabilization or regression of signs of puberty, and effects on bone age and growth rate will be studied.

### **4.3.1 Primary Efficacy Endpoint**

The primary efficacy endpoint is the proportion of subjects with suppression of GnRHa-stimulated LH (< 4 mIU/mL) at Week 24 after the first dose of study drug but before the Week 24 dose. The null hypothesis is that less than 75% of subjects will achieve suppression of GnRHa-stimulated LH (< 4 mIU/mL) at Week 24.

### **4.3.2 Secondary Efficacy Endpoints**

The following key secondary efficacy endpoints will be summarized:

- Proportion of subjects with suppression of GnRHa-stimulated LH (< 4 mIU/mL) at Weeks 12, 20, 24, 44, and 48.
- Proportion of female subjects with suppression of basal estradiol to < 20 pg/mL at Weeks 12, 20, 24, 44, and 48.
- Proportion of male subjects with suppression of testosterone to < 30 ng/dL at Weeks 12, 20, 24, 44, and 48.
- Proportion of subjects with maintenance of suppression of GnRHa-stimulated LH (< 4 mIU/mL) at Weeks 72, 96, 120, and 144.
- Proportion of female subjects with maintenance of suppression of basal estradiol to < 20 pg/mL at Weeks 72, 96, 120, and 144.
- Proportion of male subjects with maintenance of suppression of testosterone to < 30 ng/dL at Weeks 72, 96, 120, and 144.
- Proportion of subjects with suppression of the physical signs of puberty (breast development in females; testicular or genital development in males) at each scheduled assessment using modified Tanner staging.
- Incremental growth rate (cm/year) at each scheduled assessment.
- Ratio of change from Baseline in bone age to change from Baseline in chronological age at each scheduled assessment.

#### **4.3.3 Other Efficacy Endpoints**

The following other efficacy endpoints will be summarized:

- Peak stimulated LH concentrations at each scheduled assessment (not already specified in Section 4.3.2).
- Number and percentage of subjects who fail suppression of peak stimulated LH per primary endpoint analysis at each scheduled assessment.
- Number and percentage of female subjects with menstrual bleeding.
- Change from baseline in basal and peak stimulated LH, FSH, as well as basal and stimulated estradiol (for females) and testosterone (for males), to each scheduled assessment.
- Ratio and change from baseline in the ratio of bone age to chronological age at each scheduled assessment.
- Regression or no progression in pubic hair in both females and males.
- Change from baseline in uterine length, uterine volume, and ovarian volume to each scheduled assessment.
- Number and percentage of subjects with endometrial stripe presence by baseline endometrial stripe presence status (yes/no) at each scheduled assessment.
- Change from baseline in testicular length (cm), penile length (cm), and penile width (cm) by physical examination, and in testicular volume by Prader beads to each scheduled assessment.
- Change from baseline in BMI standardized score to each scheduled assessment
- Change from baseline in height standardized score to each scheduled assessment
- PedsQL and PROMIS questionnaires at each scheduled assessment.

#### **4.3.4 Safety Endpoints**

Safety evaluations are adverse events, physical examinations, vital sign measurements, LA 45 mg injection site reactions, hormonal flare and acute-on-chronic (AOC) response, and clinical laboratory testing as measures of safety and tolerability for the duration of the entire study.

#### **4.4 Sample Size Justification**

No formal sample size calculation was performed. Based on previous studies and historical precedent used for registration ( $n = \sim 40$ ), 40 subjects are sufficient to support the safety and efficacy for this class of compounds in this patient population. The planned sample size of 40 subjects will provide an observed response rate (of suppression of peak stimulated LH) that is within 16.7% of the true response rate with 95% confidence.

#### **4.5 Interim Analysis**

No interim analysis will be performed.

#### **4.6 End of Part 1 Analysis**

At the end of Part 1, an analysis of the primary, secondary and other efficacy variables collected during part 1 of the study, along with demographic and safety variables, will be performed after the last subject completes the Week 48 assessment. These analyses will include data collected during Part 1 and should not include data collected during Part 2 or during the Follow-Up Period with the exception that Week 48 may include limited data after Week 48 dose if the data is considered as Week 48. The database will be versioned for an interim soft lock and any discrepant data will be clarified before the versioning. Analyses will be performed by AbbVie.

#### **4.7 End of Part 2 Analysis**

At the end of Part 2, an analysis of the appropriate efficacy and safety variables will be performed after the last subject completes the study. Analyses will be performed by AbbVie.

#### **4.8 Multiplicity Testing Procedures for Type-I Error Control**

There will be no adjustment for multiple endpoints as there is no hypothesis being tested.

#### **4.9 Missing Data Imputation**

Unless otherwise stated, data will be summarized as observed, i.e., missing data will not be imputed.

For the endpoint of suppression of GnRHa-stimulated LH, subjects who received study drug at the Day 1 visit and are missing GnRHa-stimulated LH results at a scheduled visit in Part 1 will be counted as LH suppression failures for that visit.

### **5.0 Analysis Populations and Important Subgroups**

#### **5.1 Analysis Population**

The Full Analysis Set (FAS) consists of all subjects who received at least 1 dose of study drug. The FAS will be used for all efficacy and baseline analyses.

The safety Analysis Set consists of all subjects who received at least 1 dose of study drug.

#### **5.2 Subgroup Analysis**

Analysis of the primary efficacy endpoint will be conducted for the following subgroups by previous GnRHa treatment status and combined:

- Sex (males, females)
- Race (White, Black, or Other)
- Baseline LH value ( $< 4$  mIU/mL,  $\geq 4$  mIU/mL)
- Time between onset of puberty and start of treatment (( $\leq$  Median,  $>$  Median))
- Age at onset of puberty ( $\leq$  Median,  $>$  Median)
- Predicted adult stature compared to lower bound of range of target height ( $<$ ,  $\geq$ )
- Baseline BMI SD score ( $\leq$  Median,  $>$  Median)

## **6.0 Study Drug Duration**

Duration (days) of treatment will be summarized for the Safety Analysis Set using the number of subjects treated, mean, standard deviation, median, minimum, and maximum.

Study drug duration will be summarized as follows:

### **Part 1 of the Treatment Period:**

Last day of study drug for Part 1 – First dose date for Part 1 + 1

### **Part 2 of the Treatment Period:**

Last day of study drug for Part 2 – First dose date for Part 2 + 1

In addition, the number and percentage of subjects will be summarized separately for Part 1 and Part 2 for the following categories:

- Number of injections that each subject received (1 or 2)
- Compliance or non-compliance with the dosing scheme. A subject will be considered non-compliant with the dosing scheme if there was a gap larger than 3 days gap between the last day of one injection and the day of the next injection.

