 INTERVIEW	
 Menstrual bleeding calendar (females) Adverse event assessment Concomitant therapy
 EXAM	
 Height (in triplicate) and weight Brief physical examination Vital signs
 LAB	
 Estradiol (females) Testosterone (males) LH and FSH GnRHa stimulation test Leuprolide concentration (first 20 subjects only)

WEEK 12 VISIT (\pm 6 days):

 INTERVIEW	
 Menstrual bleeding calendar (females) Adverse event assessment Concomitant therapy
 PRO	
 PedsQL and PROMIS questionnaires
 EXAM	
 Height (in triplicate) and weight Brief physical examination Vital signs
 LAB	
 Safety laboratory tests (hematology and chemistry) Estradiol (females) Testosterone (males) GnRHa stimulation test LH and FSH Leuprolide concentration (first 20 subjects only)

WEEK 20 VISIT (\pm 6 days):

 INTERVIEW	
 Menstrual bleeding calendar (females) Adverse event assessment Concomitant therapy
 EXAM	
 Height (in triplicate) and weight Brief physical examination Vital signs
 LAB	
 Estradiol (females) Testosterone (males) LH and FSH GnRHa stimulation test Leuprolide concentration (first 20 subjects only)

Week 24 VISIT (\pm 6 days):

 INTERVIEW	
 Hormonal flare and AOC response assessment Menstrual bleeding calendar (females) Adverse event assessment Concomitant therapy LA 45 mg injection site reaction assessment
 PRO	
 PedsQL and PROMIS questionnaires
 EXAM	
 Bone age radiograph Height (in triplicate) and weight Complete physical examination Vital signs Pubertal staging (modified Tanner) (all subjects) Penile length and width and testicular length and volume (males) Transdermal pelvic ultrasound (uterine and ovarian volume) (females)
 LAB	
 Safety laboratory tests (hematology and chemistry) Estradiol (females) Testosterone (males) GnRHa stimulation test LH and FSH Leuprolide concentration (first 20 subjects only)
 TREATMENT	
 LA 45 mg 6-month

WEEK 24 + 48 HOURS VISIT (\pm 24 hours) (48 HOURS POST INJECTION):

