2.2 Individual Treatment Period Visit Activities (Part 2)

Week 48 VISIT (\pm 6 days):

START OF PART 2^{a,b}

 INTERVIEW	
 • Hormonal flare and acute-on-chronic (AOC) response assessment • Leuprolide acetate (LA) 45 mg injection site reaction assessment
 TREATMENT	
 • LA 45 mg 6-month

a. Week 48 is the end of Part 1 and the start of Part 2.
b. At the beginning of Part 2, using the interactive response technology (IRT) system, half of the subjects will be randomly selected to have visits for AOC biochemical assessment 48 hours after the injection of study drug at Weeks 48, 72, 96, and 120. Subjects who are not randomly selected for the AOC biochemical assessments will have phone contacts 1 day after the injection of study drug at Weeks 48, 72, 96, and 120.

WEEK 48 + 1 DAY PHONE CALL (\pm 2 days) TO PARENT OR LEGAL GUARDIAN:^a

 INTERVIEW	
 • Hormonal flare and AOC response assessment • Adverse event assessment • Concomitant therapy • LA 45 mg injection site reaction assessment
a. Does not apply to those subjects who are randomly selected for AOC biochemical assessment.	

WEEK 48 + 48 HOURS VISIT (\pm 24 hours) (48 HOURS POST INJECTION):^a

 INTERVIEW	
 • Hormonal flare and AOC response assessment • Adverse event assessment • Concomitant therapy • LA 45 mg injection site reaction assessment
 LAB	
 • Luteinizing hormone (LH) and Follicle-stimulating hormone (FSH) • Estradiol (females) • Testosterone (males)
a. Applies only to subjects who are randomly selected for AOC biochemical assessment.	

WEEK 48 + 7 DAYS PHONE CALL (\pm 2 days) TO PARENT OR LEGAL GUARDIAN:

 INTERVIEW	
 • Hormonal flare and AOC response assessment • Adverse event assessment • Concomitant therapy
--	---

WEEK 72 VISIT (\pm 6 days):

 INTERVIEW	
 • Hormonal flare and AOC response assessment • Menstrual bleeding calendar (females) • Adverse event assessment • Concomitant therapy • LA 45 mg injection site reaction assessment
 PRO	
 • Pediatric Quality of Life Inventory (PedSQL) and Patient Reported Outcomes Measurement Information System (PROMIS) questionnaires

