3.19 Administration of Study Drug

Study drug will be administered to subjects beginning at Baseline (Day 1) and at the time points specified in Section 2 as follows:

Part 1: LA 45 mg 6-month, given as a single intramuscular injection. The first injection will be administered on Day 1, and the second injection will be administered at Week 24.

For subjects who were previously treated with GnRHa therapy, the first injection of study drug should be administered at the end of the previous GnRHa treatment cycle.

Part 2: LA 45 mg 6-month, given as a single intramuscular injection at 24-week intervals (up to 24 months) starting at Week 48 until Week 120.

Study site staff will administer all injections of LA 45 mg 6-month. Each injection of study drug should be administered in the gluteal area, anterior thigh, or deltoid. Injection sites should be alternated to minimize injection site reactions.

If a subject cannot come to the site because of unforeseen circumstances (e.g., the COVID-19 pandemic), the injection of study drug may be administered by a home healthcare nurse at the subject's home. AbbVie should be notified if this occurs.

Refer to Section 7.3 for dose preparation instructions.

Depending on local regulations, provisioning of study drug and generic LA for stimulation test for direct-to-patient (DTP) and direct-from-patient (DFP) transfer because of unforeseen circumstances (e.g., the COVID-19 pandemic) will be available upon request. AbbVie should be notified if this occurs. Sites can use Marken, a third-party vendor with which AbbVie has an agreement, for drug shipment in these circumstances or sites may use a local courier.

Sites will be responsible for meeting IRB reporting requirements and submitting the booking form (which will be provided) to the local IRB (as applicable).

The investigator must discuss the DTP process with the subject's parent or legal guardian:

- Obtain consent to provide delivery information to Marken and/or local courier and record this in source documentation.
- Obtain and review results of required safety procedures as applicable before registering subject dispensation of study drug in interactive response technology (IRT).
- Confirm that the subject's parent or legal guardian will be available to accept delivery.
- The site will follow-up with the subject's parent or legal guardian after shipment is received.

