6 STUDY DRUG

6.1 Treatments Administered

Study drug (LA 45 mg 6-month) will be administered at the visits listed in Section 2. LA 45 mg 6-month drug product will be injected intramuscularly once every 24 weeks. Each injection should be administered in a different anatomical site to minimize injection site reactions.

LA 45 mg 6-month drug product will be provided by AbbVie as a pre-filled dual chamber syringe containing sterile lyophilized microspheres, which when mixed with diluent, become a suspension

intended for intramuscular injections to be given once every 24 weeks. The front chamber of the LA formulation pre-filled dual chamber syringe contains LA (45 mg), and the second chamber contains diluent. Study drug must be prepared as described in the instructions for drug preparation (refer to Section 7.3).

Study drug must not be administered without contacting the IRT system. Study drug may only be administered to subjects enrolled in the study through the IRT system. If a subject cannot come to the site because of unforeseen circumstances (e.g., the COVID-19 pandemic), the site may contact the IRT for kit assignment. Study drug can then be dispensed as described in Section 3.19.

At the end of the Treatment Period or at the Premature Discontinuation Visit, the site will contact the IRT system to provide visit date information.

The GnRHa stimulation test will be conducted using generic LA aqueous solution. For the stimulation test, 20 µg/kg of generic LA aqueous solution will be administered subcutaneously. Generic LA aqueous solution will be supplied to the sites for the purpose of conducting the stimulation test. Each site will be responsible for maintaining drug accountability records, including product description, manufacturer, lot numbers, and administration to subjects. Sites should use their standard of care practice for preparation of the injection site and injection of generic LA aqueous solution. If a subject cannot come to the site because of unforeseen circumstances (e.g., the COVID-19 pandemic), the GnRHa stimulation test may be performed by a home healthcare nurse at the subject's home.

There may be times when the sponsor is unable to provide the generic LA aqueous solution. Under these circumstances, the participating sites have the option to obtain this product through an external licensed pharmacy or wholesaler or from local site supplies.

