## **9.2 Analysis of Adverse Events**

### **9.2.1 Treatment-Emergent Adverse Events**

Treatment emergent adverse events are defined as any event with an onset date that is after the first dose of study drug and with an onset date no more than 12 weeks after the end of the effect of study drug (24 weeks after the date of the last administration of study drug). Events where the onset date is the same as the study drug start date are assumed to be treatment emergent.

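### SAP 6.0 allows only 1 or 2 injections in Part 2, where four are scheduled, and its compliance rule starts from an undefined last day of an injection

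*SAP*

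**What the plan says.** SAP Section 6.0 (Study Drug Duration) gives a duration formula for each part and then two categorical summaries. Its lead-in covers both parts: "the number and percentage of subjects will be summarized separately for Part 1 and Part 2 for the following categories". The first item is the "Number of injections that each subject received (1 or 2"). The second is compliance with the dosing scheme: a child is non-compliant "if there was a gap larger than 3 days gap between the last day of one injection and the day of the next injection".

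The dosing schedule is in the Operations Manual (Protocol Appendix F). Section 3.19 puts the Part 1 injections on Day 1 and at Week 24. The Part 2 injections are "given as a single intramuscular injection at 24-week intervals (up to 24 months) starting at Week 48 until Week 120". Section 6.1 states the interval: "LA 45 mg 6-month drug product will be injected intramuscularly once every 24 weeks". Sections 2.1 and 2.2 allow plus or minus 6 days at the Week 24, 48, 72, 96 and 120 visits, at which these later doses are given.

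**The concern.** There are two separate defects.

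- **Injection count.** The categories 1 and 2 are applied to both parts, and nothing marks them as examples or limits them to Part 1. Programmed as written, the Part 2 table cannot place a child who received the planned treatment.
- **Compliance rule.** An injection happens on one day, so its last day needs a definition, and neither document supplies one. The duration formulas in the same section use a similar term, the last day of study drug, which is also undefined. The compliance table therefore depends on what the programmer assumes. On the most sensible assumption, some doses inside the protocol's visit window are still reported as non-compliant, and the reader is not told that a stricter standard is in use.

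At stake is whether the exposure and compliance tables describe dosing correctly. They matter somewhat here because the study is meant to assess whether a 24-week interval suits this formulation (Protocol 4.1, SAP 4.2.1).

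**Working it through.** **Injection count**

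1. Part 1 has doses at Weeks 0 and 24, which is 2. The SAP's 1 or 2 is reproduced for this part.
2. Part 2 has doses at Weeks 48, 72, 96 and 120, which is 4. SAP 4.2.2 names the same four injection weeks.
3. The Week 48 dose belongs to Part 2. Protocol Appendix D assigns to Part 1 only the Week 48 activities that come before the third dose, and Operations Manual 2.2 lists that dose under the start of Part 2.
4. Among children dosed in Part 2 the possible counts are 1, 2, 3 and 4, and the SAP has a category for 2 of these 4. A child whose last dose is at Week 96, with none missed, has 3. A fully dosed child has 4.
5. Zero is also possible. The Safety Analysis Set requires one dose in the study, not one in each part, so a child who stops drug in Part 1 belongs to the set with no Part 2 injection.

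**Compliance rule at Week 24**

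Inputs: Week 0 is Day 1 (Protocol Figure 1 notes); the interval is 24 × 7 = 168 days; the window is plus or minus 6 days. Week 24 is therefore Day 1 + 168 = Day 169, and the permitted days are 163 to 175, 13 in all. Let *o* be the number of days from schedule, from −6 to +6. The rule flags a gap above 3 days.

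| Meaning given to the last day | Gap in days | Permitted days flagged |
|---|---|---|
| Injection date | 168 + *o* = 162 to 174 | 13 of 13 |
| Injection date + 168 | *o* = −6 to 6 | 3 of 13 (4, 5, 6 days late) |
| Injection date + 167 (day before the next dose is due) | *o* + 1 = −5 to 7 | 4 of 13 (3, 4, 5, 6 days late) |

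The second reading has the best support. It matches the 24-week interval, and SAP 9.2.1 places the end of drug effect "24 weeks after the date of the last administration of study drug". That sentence serves the adverse event window, however, and SAP 6.0 does not refer to it. The third row shows that even a one-day difference in convention changes who is flagged.

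These are counts of permitted dates, not expected frequencies. The documents give no distribution of visit timing.

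**The case against.** The strongest reply is that both items are slips any programmer would repair. SAP 4.2.2 names four Part 2 injections, so rows 3 and 4 would be added. Nobody would program the injection-date reading, because no child with two doses could then comply. A drug-coverage limit and a visit window also answer different questions, so a 3-day limit beside a 6-day window is not in itself an error.

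Much of this stands. It keeps the point minor, and it is a reason to retain the 3-day rule. It does not remove the need for a definition, since the plausible coverage conventions still disagree, or for a label saying that the rule is stricter than the window.

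A reader might infer more than the documents support:

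- *Every child who completes Part 2 is unclassified.* Protocol 5.5 asks that children who stop study drug stay in follow-up. A child can complete the Part 2 visits after only 1 or 2 Part 2 injections and would have a category. The statement holds for fully dosed children.
- *The efficacy results are affected.* The LH suppression denominators use receipt of the Day 1 dose (SAP 8.2, 8.3). The sex steroid denominators use whether the prior scheduled injection was given (SAP 8.3). The treatment-emergent window uses the last administration date (SAP 9.2.1), and the analysis sets require one dose. None uses the count table or the 3-day rule.
- *A flag rate for later pairs of doses can be calculated.* That requires knowing whether visits stay anchored to Day 1 after a late dose or are re-timed from the previous one. The dosing and visit-window sections do not say.

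**Conclusion.** The point holds, with minor severity. The Part 2 injection categories contradict the schedule: 2 of the 4 counts possible among children dosed in Part 2 have a category, and every fully dosed child falls outside them. The number of children affected cannot be calculated because the documents give no Part 2 retention figure.

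The compliance rule is incomplete. At Week 24 it flags 13 of 13 permitted days if the last day is the injection date, and 3 of 13 if it is dose plus 168 days. The second figure assumes that coverage lasts exactly 24 weeks, which is supported by Operations Manual 6.1 and, by analogy, SAP 9.2.1. The 3-day limit can stand once it is defined and labelled. The consequences are confined to descriptive exposure and compliance tables.

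**What to change.** Revise SAP Section 6.0 as follows:

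1. Keep 1 and 2 as the Part 1 categories. For Part 2 use 1, 2, 3 and 4 among children dosed in Part 2, or 0 to 4 if the denominator is the full Safety Analysis Set, and state which.
2. Define the last day of an injection as its administration date plus 168 days.
3. Keep the 3-day rule, but label it as a drug-coverage measure stricter than the visit window.
4. Beside it, report the number and percentage of children dosed within the protocol's plus or minus 6-day window.

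Optionally, state whether the interval from Week 24 to Week 48 counts in Part 1 or Part 2, since it spans both.

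The cost is SAP wording and small changes to table shells. The injection dates are already collected.
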